6.1.1 Sensitivity to Covariate Adjustment

Where feasible, we will also perform analysis using different covariate sets that includes as possible adjustment variables the set above as well as other covariates. These additional covariates include but are not limited to:

- 1) Whether the patient lives in a rural or urban area (based on RUCA codes)
- 2) Whether the hospital is in a rural or urban area (based on RUCA codes)
- 3) Whether the patient had a rehabilitation referral at discharge (physical therapy, occupational therapy, or speech therapy)
- 4) Whether the patient had a home health referral at discharge
- 5) Whether the patient had a documented PCP in their medical record
- 6) Dual eligibility for Medicaid (FFS analyses only)
- 7) History of depression
- 8) History of hypertension
- 9) History of smoking
- 10) History of CVD comorbidities

Covariates listed above will be ascertained as part of the COMPASS study and not from claims. Variables will be selected for inclusion in the sensitivity analysis model using a backward selection procedure that accounts for missing covariate data using methods described in Section 6.5. The sensitivity model will include key clinical covariates as well as any of the above variables that have a p-value > 0.10 (unadjusted for multiple comparisons). Estimates of treatment effects will be produced for each step in the model selection procedure to understand how effect estimates change based on different adjustment sets.

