- 5). Phase 2: Using Claims, the Sustainability analyses compared outcomes in hospitals randomized to deliver the INV in Phase 1 with outcomes among those that sustained the intervention (SUS) in Phase 2 for mortality; health care utilization; (emergency department visits, admissions to skilled nursing facilities/inpatient rehabilitation

Application - IRB00035998

facilities); and use of transitional care management billing codes. We will use claims data from multiple payer sources up to 12 months after stroke hospitalization.

Data Collected for Ancillary Studies:

- 1) Analysis of individual, organizational, and community factors affecting implementation of COMPASS through supplemental funding (CTSI Award lead by Co-I [name]). This pilot project will contribute to a process evaluation of our Phase1, intervention-randomized health systems adopting COMPASS.
- 2) An exploratory analysis that compares patient clinic return rate and use of services to physical locations of patients and services (i.e. distance and drive times to/from clinics and community resources).
- 3) At the 90 day survey, we will also use the PROMIS Global-10 instrument that assesses general domains of health and functioning including overall physical health, mental health, social health, pain, fatigue, and perceived quality of life. These are similar in nature to our primary outcome, the SIS-16.

Hospital Performance Metrics (to support participating sites in delivery of the intervention):

1) Evaluate compliance with the new model of post-acute stroke care by exploring quality indicators among intervention hospitals, (e.g., proportion of patients called within 2 days after hospital discharge; proportion of patients seen by an advanced practice provider [MD/NP/PA] within 7 to 14 days from hospital discharge; and proportion of eligible patients receiving home or outpatient rehabilitation therapy).

Methods and Measures

Study Design

The COMPASS Study is a pragmatic, cluster-randomized trial of 41 hospitals in North Carolina designed to determine the effectiveness of a model of post-acute stroke care (i.e. the COMPASS Intervention) compared with usual care (Control).

Study Setting

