If the patient is eligible, they will be enrolled in a similar manner to that of the Control patients: The PAC will visit each patient in the hospital and give the patient a tailored handout about the COMPASS Study (Appendix 12). The information informs the patient that their hospital is participating in a state-wide study to evaluate best models of post stroke care. The patient will be informed if their hospital is in the usual care group or in the COMPASS intervention group. This brochure is tailored to the hospital. The PAC name and the PAC contact information will be provided on an appointment card. This information will equip patients with information to fully inform them of the COMPASS Study and how this will impact them and what to expect from the hospital. The PAC will also give an additional handout about COMPASS

Application - IRB00035998

intervention activities (Appendix 13), a Blood Pressure Log (Appendix 14) and Blood Pressure Handout (Appendix 15). The PAC will work with the patient to schedule follow-up visits with the patients Primary Care Physician (PCP) and the Advanced Practice Provider (APP) for the 7-14 day follow-up visit. The PAC will let the patient know they will be calling them in a couple of days for the 2-day follow-up phone call. The PAC will record patient and caregiver contact information on the COMPASS enrollment form. In the COMPASS analytical database, the PAC will record the date, time and method (i.e. in person or over the phone) of informing the patient of the COMPASS Study, and confirm that the patient was given the brochure. As a pragmatic study, we anticipate that PACs may miss a patient (for example a patient may be missed on the weekends) and the patient will need to be enrolled retrospectively and notified of the study and mailed the brochure. The PAC will attempt to reach the patient over the phone to follow-up on the mailed brochure. The brochure also has contact information for the patient to call the study if they would like additional information.

As part of case ascertainment and consistent with the North Carolina Stroke Care Collaborative methodologies to characterize all stroke admissions and processes of acute stroke care the PAC will complete the NC Stroke Care Card (Appendix 9). (Note: this is identical to the Control group).

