PM4. Receipt of all home health and outpatient rehabilitation services (including physical therapy, occupational therapy, and speech and language therapy) prescribed at hospital discharge, 2-day follow-up call, or 7-14-day follow-up clinic visit by 30-days after hospital discharge				х	
PM5. Receipt of all home health rehabilitation services (including physical therapy, occupational therapy, and speech and language therapy) prescribed at hospital discharge, 2-day follow-up call, or 7-14-day follow-up clinic visit by 30-days after hospital discharge				Х	
PM 6. Receipt of all outpatient rehabilitation services (including physical therapy, occupational therapy, and speech and language therapy) prescribed at hospital discharge, 2-day follow-up call, or 7-14-day follow-up clinic visit by 30-days after hospital discharge				Х	
Characteristics of enrolled health systems (size, location, Comprehensive Stroke Center certification)			Х		
Characteristics of PAC teams (number of FTE, license, etc)			Х		
Characteristics of Community Resource Networks			Χ		
Characteristics of clinical staff participating in bi-weekly problem solving calls			Х		
Challenges with enrollment, 2 day call, 14 day visit, e care plan, receipt of therapy, community resource network, administrative tasks				Х	
Requests for additional training				Х	
Time it takes to integrate COMPASS components into system (ramp up)					Х
What are sites doing to maintain COMPASS? What are they changing? Are they returning to their original model of care?					Х
*90-day outcomes and claims data are part of the COMPASS trial, not this pilot		*X			
PM = Performance Measure	1		1	1	

March 19, 2021 Application - IRB00035998 Appendix 34 – 2Day Disposition Form

ID Number:	Form Code: C D S P Date: 07JUN2016 Version 1.0
ADMINISTRA	Date: Day
Did you c hospital?	complete a follow-up call with the patient or caregiver after the patient was discharged from the
	s → Go to Q1a
□ No	→ Go to Q1b
	Month Day Year
2b. Reas	son for no follow-up call:
	□ Did not attempt call
	☐ Could not reach patient/caregiver after 2 attempts
	□ Patient/caregiver refused
	 □ Patient/caregiver could not complete (e.g. confused, unable to communicate, too sick, etc.) □ Patient/caregiver did not have workable number
	☐ Patient hospitalized
	☐ Patient transferred to a skilled nursing facility
	□ Patient deceased
	□ Other (specify)
	END OF 2-DAY CALL DISPOSITION FORM

March 19, 2021 Application - IRB00035998 Appendix 35 – Clinic Disposition Form

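### SAP 6.1.1 puts rehabilitation and home-health referral at discharge among the baseline adjustment candidates, although COMPASS could plausibly change both, so Phase 1 sensitivity models containing them may not estimate the ITT effect

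*SAP*

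**What the plan says.** SAP 6.1 fixes the main covariate set: arm or phase, race, age, index diagnosis, NIHSS category, sex, prior stroke and prior TIA. SAP 6.1.1 then offers ten further candidates for a backward-selection sensitivity model. Items 3, 4 and 5 are "Whether the patient had a rehabilitation referral at discharge (physical therapy, occupational therapy, or speech therapy"), "Whether the patient had a home health referral at discharge" and "Whether the patient had a documented PCP in their medical record". The other seven are rurality of patient and of hospital, dual eligibility, and histories of depression, hypertension, smoking and cardiovascular disease. On source and use, the section says "Covariates listed above will be ascertained as part of the COMPASS study and not from claims" and "Estimates of treatment effects will be produced for each step in the model selection procedure", so as to see how the effect moves with the adjustment set. It does not separate characteristics fixed before the intervention can act from care that the arm might alter.

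SAP 5.1 defines the Phase 1 comparison by assigned arm, whether or not the patient received any part of the intervention. The Protocol (Randomization) randomises hospitals, so every index discharge follows randomisation.

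**The concern.** An ITT effect by arm includes whatever the arm does through referral. If COMPASS hospitals refer more (or fewer) patients to rehabilitation or home health, a model holding referral fixed answers a different question, and two distortions can follow.

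- **Mediation.** Any benefit that runs through referral is adjusted away.
- **Selection within strata.** Referral depends on need. If one arm refers more readily, patients with equal referral status no longer have equal need across arms. A difference can then appear where none exists.

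Backward selection starts from the full candidate set, so at least the first step contains both referral items. SAP 6.1.1 plans to report an effect at each step. A shift between steps would be taken as information on covariate imbalance when it could be adjustment bias. The section plans no by-arm table of these items, so a reader could not tell which.

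**Working it through.** **Step 1. Can the arm change these items?** Coming after hospital randomisation does not settle it, because every patient-level covariate does, NIHSS included. What matters is whether the arm can move the variable.

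- *In favour.* The Protocol (Intervention and Interactions) states the goal as organising post-acute care processes. Intervention work begins before discharge: "The PAC will work with the patient to schedule follow-up visits with the patients Primary Care Physician (PCP") and with the advanced practice provider. Hospital Performance Metrics includes the "proportion of eligible patients receiving home or outpatient rehabilitation therapy". Appendix 33 (PM4 to PM6) tracks rehabilitation services "prescribed at hospital discharge, 2-day follow-up call, or 7-14-day follow-up clinic visit by 30-days after hospital discharge".
- *Against.* The intervention section names no in-hospital rehabilitation or home-health referral, and it describes clinic-visit referrals as additional. PM4 to PM6 measure receipt of services already prescribed. Control coordinators complete the same Enrollment Form.

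An arm effect on discharge referral is therefore plausible but inferred.

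**Step 2. Size if the arm does shift referral.** The plan gives no figure to reproduce and no referral rates, so this is an illustration. Let A be arm (1:1), U unmeasured need (half of patients), M referral and Y 90-day readmission:

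- logit P(M=1) = m₀ + s·A + ln(OR_UM)·U
- logit P(Y=1) = c + ln(OR_UY)·U + ln(OR_MY)·M + ln(OR_AY)·A

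From the documents: control readmission of 25% (Protocol, Background), which sets c. Assumed: control referral of 50%, shifts of 0, 5, 10 and 20 points, and the odds ratios shown below. Logistic models of Y on A, and of Y on A and M, were fitted to the exact population.

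| Case (OR_UM, OR_UY, OR_MY, OR_AY) | Shift | OR without M | OR with M | Ratio |
|---|---|---|---|---|
| Any | 0 | unchanged | unchanged | 1.000 |
| (a) Effect only through referral (1, 1, 0.7, 1) | +5 | 0.982 | 1.000 | 1.018 |
| | +10 | 0.965 | 1.000 | 1.036 |
| | +20 | 0.930 | 1.000 | 1.075 |
| (b) No effect at all, shared cause (3, 3, 1, 1) | +5 | 1.000 | 0.986 | 0.986 |
| | +10 | 1.000 | 0.972 | 0.972 |
| | +20 | 1.000 | 0.945 | 0.945 |
| (c) Mixed (3, 2, 0.7, 0.85) | +5 | 0.838 | 0.845 | 1.008 |
| | +10 | 0.824 | 0.837 | 1.017 |
| | +20 | 0.795 | 0.822 | 1.034 |

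*Case (a), +20, by hand.* A 25% average at 50% referral with OR 0.7 gives risks of 28.33% (not referred) and 21.67% (referred). Intervention risk = 0.30 × 0.2833 + 0.70 × 0.2167 = 0.2367. OR = (0.2367/0.7633) / (0.25/0.75) = 0.930. Within each referral stratum the arms are identical, so the adjusted OR is 1.

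*Case (b), +20, by hand.* Risks are 34.86% with high need and 15.14% without. High need makes up 63.4% of referred control patients but 57.9% of referred intervention patients; among the unreferred it is 36.6% and 31.5%. Risks among the referred are 27.64% and 26.57% (OR 0.947), and among the unreferred 22.36% and 21.35% (OR 0.942). Pooled, this gives 0.945 when the truth is 1.

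**Step 3. Stronger assumptions.** Take U as standard normal, logit P(M=1) = −0.45 + m·A + U (control referral 41%), logit P(Y=1) = −1.2 + b·U, and no arm or referral effect. The OR without M is 1.00. With M it is:

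| Shift | b = 0.5 (risk 24%) | b = 1.0 (risk 27%) |
|---|---|---|
| 0 | 1.00 | 1.00 |
| +5 | 0.98 | 0.96 |
| +10 | 0.961 | 0.929 |
| +15 | 0.942 | 0.896 |
| +20 | 0.923 | 0.865 |

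**The case against.** The strongest reply is that nothing in the documents shows COMPASS altering discharge referral. The four intervention components all follow discharge, and the coordinator's extra in-hospital tasks are handouts, the blood pressure log and scheduling visits. The performance measures reward delivery of prescribed services, and prescribing more does not by itself raise the score. All of this stands. A reader might infer that COMPASS itself acts on discharge referral and that the sensitivity estimates are therefore biased. The documents support only that this could happen.

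A reader might also treat a documented primary care provider as a discharge-care step. That goes too far. Scheduling a visit (Enrollment Form item 31) differs from having a provider (item 32), and the Protocol's wording on scheduling presupposes that the patient has one. It is largely a pre-existing attribute and a plausible confounder, notably for the continuity-of-care endpoint. The remaining doubt is when it was recorded.

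It can further be said that referral stands in for functional impairment that NIHSS misses, and that the Protocol (Analytical Plan) expects patient-level imbalances. This has some force. But NIHSS is already in every model, and the Enrollment Form (item 22) records ambulatory status before admission, which the arm cannot affect. The proxy argument therefore does not justify leaving referral unmarked in the ITT selection path. It has more weight for the Phase 2 between-phase comparisons, which are not randomised, so the change proposed here is confined to Phase 1.

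Finally, this SAP is an addendum to a Phase 1 SAP that is not among the documents, and a rationale for these covariates may be given there.

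**Conclusion.** The point holds as a limited one. SAP 6.1.1 mixes two discharge-care decisions with baseline characteristics, and Phase 1 sensitivity models containing them may not estimate the total effect by assigned arm that SAP 5.1 sets out. Over shifts of 5 to 20 points the two-level illustration gives a distortion of about 1 to 8% on the odds ratio scale, in either direction. The stronger-link model reaches 0.865 against a true 1.00, but only with a 20-point shift and the strong severity link. With no shift there is no bias. Apart from the 25% readmission rate, every input is assumed.

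The main analyses in SAP 6.2 and 6.3 use the 6.1 covariates and are not touched. A reader might conclude that the trial's claims results are compromised; the documents do not support that. What is at risk is the interpretation of a robustness check. The p-value rule for retaining variables in 6.1.1 is a separate matter, and correcting it would not resolve this one.

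**What to change.** In SAP 6.1.1, for the Phase 1 ITT sensitivity model:

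1. Remove items 3 and 4 (rehabilitation and home-health referral at discharge) from the backward-selection candidates.
2. Tabulate both by arm, so that any shift is visible.
3. If they are modelled, do so in a separate exploratory analysis labelled as adjusting for care the arm may have affected, and not as a robustness check on the ITT effect.
4. If a further severity proxy is wanted, use pre-admission ambulatory status from the Enrollment Form.
5. Keep item 5 if it is defined as a primary care provider recorded before the index admission; otherwise treat it like items 3 and 4.

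The cost is a wording change and one table, with no new data for items 1 to 4. The downside is that the sensitivity model loses a partial proxy for functional impairment at discharge, which pre-admission ambulatory status only partly replaces.

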5 CLAIMS ANALYSES

5.1 Phase 1 Intent-to-Treat Analyses

We will perform intent-to-treat analyses comparing the COMPASS intervention to UC with respect to all endpoints listed in Table 1 stratified by insurance provider (i.e., FFS Medicare, NC Medicaid (excluding patients with dual Medicare coverage), BCBS-NC). Comparisons will be made based on the intervention arm to which a patient belongs regardless of whether the patient received any intervention. For intent-to-treat analyses, all individuals must have been enrolled at the time of the index discharge event in one or more of the insurers (CMS Medicare, NC Medicaid, or BCBSNC). The FFS Medicare analysis population will include participants enrolled in CMS Medicare Parts A & B. Participants only enrolled in Part A or those enrolled in Part C (Medicare Advantage) will be excluded. The Medicaid analysis population will include participants enrolled in a qualifying Medicaid plan. Examples of non-qualifying plans include plans only covering children, plans for pregnancy-related care, cancer-related care, or those covering emergency services only. Participants dually enrolled in Medicaid and Medicare will be excluded from the Medicaid analyses. The BCBS analysis population will consist of participants enrolled in BCBS of NC, not also enrolled in Medicare.

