6.1 Covariate Adjustment

Unless otherwise stated below, where feasible the following covariates will be incorporated in analysis models for all endpoints described in Table 1.

- 1. Study Arm (intervention, usual care) ITT Phase 1 analyses only
- 2. Study Phase (sustainability, intervention) ITT Phase 2 sustainability analyses only
- 3. Study Phase (intervention, usual care) ITT Phase 2 effectiveness analyses only
- 4. Race (non-white; white)
- 5. Age (degree two polynomial)
- 6. Index hospitalization diagnosis (stroke; TIA)
- 7. NIH Stroke Scale (NIHSS) Score category (0, 1-4, 5-15, and 16-42) categories may be collapsed to 5-42 due to sample size requirements.
- 8. Sex (female; male)
- 9. Prior stroke
- 10. Prior TIA

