6.2 Analysis of Binary Endpoints

The set of binary endpoints to which this section pertains are given as follows:

1. Incidence of 30-day all cause readmissions

- 2. Incidence of 90-day all cause readmissions
- 3. Use of TCM billing codes

For the analysis of 30- and 90-day all cause readmissions, patients who have continuous coverage over the 30- or 90-day reference period will be included in the analysis. For analysis of TCM billing codes, patients who have continuous coverage over the 30-day period following discharge from the index hospitalization will be included in the analysis. The percentage of patients with incomplete coverage over the 90-day period following discharge from the index hospitalization is expected to be low. In the event that more than 10% of the patients linked to claims data have incomplete coverage over the relevant 30- or 90-day reference period, we will assess the robustness of any important findings to exclusion of these patients from analyses using techniques such as multiple imputation from a time-to-event model that accounts for the observed follow-up period for patients who drop out of coverages during the relevant reference period.

For readmission endpoints, patients who die prior to the end of the reference period without a qualifying readmission will be treated as not having a readmission. Prior analyses of 90-day mortality based on the full COMPASS cohort has demonstrated that the percentage of patients who die within 90 days of discharge from the index hospitalization is approximately 2.0% and did not differ by treatment arm.⁴ Thus, the impact of excluding patients who did not survive for the entire reference period is not expected to strongly influence results. Nonetheless, in the event that more than 5% of the patients linked to claims data die within the reference period, we will assess the robustness of any important findings by performing a sensitivity analyses that includes these patients as having met the endpoint for all cause readmissions.

For all binary endpoints, we will employ generalized linear mixed models (GLMM) with a logistic link function. Models will include a hospital-specific random effect, and adjust for the covariates described in Section 6.1.

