6.3 Analysis of Time-to-Event Endpoints

6.3.1 One-Year Mortality Analysis

Analysis of the one-year mortality endpoint will be performed using a Cox proportional hazards model that adjusts for the covariates described in Section 6.1. Analyses will be performed using the method of Wei, et al.⁵ which models the marginal distribution for event times and account for correlation between event times within a hospital unit through use of a robust sandwich variance estimator for model parameters.

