6.5 Subgroup Analyses

It is of *a priori* interest to examine the comparative effectiveness of the COMPASS Intervention in key subgroups of the studied population. We will examine the comparative effectiveness of the COMPASS Intervention in the following subgroups for the FFS analyses, where feasible:

- Diagnosis group stroke; TIA
- Race non-white; white
- Sex female, male
- Age -- <65; 65-<75; 75-<85; >=85
- NIHSS 0, 1-4, 5-15, and 16-42

Categories may be collapsed due to small sample sizes within each subgroup.

For each of the characteristic above (e.g., race) and to the extent that samples size permits, we will evaluate the comparative effectiveness of the COMPASS Intervention against usual care within each of the corresponding subgroups (e.g., for whites and non-whites) using the following procedure.

We will first assess the degree to which the data support the assumption of a homogeneous intervention effect across levels of each subgroup. This will be done by fitting an augmented model that includes a treatment by subgroup interaction and by formally testing the interaction at significance level 0.10. If the interaction is not statistically significant at level 0.10, the analyses adjusted for, but not stratifying by, subgroup will be presented for primary interpretation. However, if the interaction is significant at level 0.10, analyses will be presented that estimate separate treatment effects for each subgroup level using a single model with the familywise type I error rate controlled using Hommel's method.⁹

Bibliography

- 1. Agency for Healthcare Research and Quality (AHRQ). Clinical Classifications Software (CCS) for ICD-10-PCS (beta version). 2019; https://www.hcup-us.ahrq.gov/toolssoftware/ccs10/ccs10.jsp. Accessed Feb 15, 2021.
- 3. Centers for Medicare and Medicaid Services (CMS). Transitional Care Management Services. 2021; https://www.cms.gov/outreach-and-education/medicare-learning-network-mln/mlnproducts/downloads/transitional-care-management-services-fact-sheet-icn908628.pdf. Accessed Feb 15, 2021.

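### SAP 6.1.1 names backward selection but states its retention rule the wrong way round, including candidates with p > 0.10

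*SAP*

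**What the plan says.** Section 6.1 gives a fixed adjustment set as the default: "Unless otherwise stated below, where feasible the following covariates will be incorporated in analysis models for all endpoints described in Table 1". The main models rely on it. For binary endpoints, "Models will include a hospital-specific random effect, and adjust for the covariates described in Section 6.1"; one-year mortality is analysed "using a Cox proportional hazards model that adjusts for the covariates described in Section 6.1".

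Section 6.1.1 adds a sensitivity analysis with ten further named candidates, in a list left open to others. They are chosen by "a backward selection procedure that accounts for missing covariate data using methods described in Section 6.5". The next sentence defines the resulting model: "The sensitivity model will include key clinical covariates as well as any of the above variables that have a p-value > 0.10", with no multiplicity adjustment of that p-value. The section also promises that "Estimates of treatment effects will be produced for each step in the model selection procedure".

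The SAP's only other significance rule at this level is in Section 6.5: "if the interaction is significant at level 0.10, analyses will be presented that estimate separate treatment effects for each subgroup level". Section 5.1 runs the comparisons "with respect to all endpoints listed in Table 1 stratified by insurance provider", and the documents give no stratum sizes.

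**The concern.** Two adjacent sentences in Section 6.1.1 cannot both be followed. Backward selection at 0.10 discards terms with p above 0.10 and ends with terms at or below it. The inclusion sentence admits the terms above 0.10. Its verb is one of inclusion, so it cannot be read as a removal criterion.

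If the sentence is followed, the sensitivity model no longer does its job. Its purpose is to show whether the treatment effect survives adjustment for candidates such as dual eligibility, rurality or cardiovascular comorbidity. A rule that favours candidates unrelated to the outcome says little about that. If the sentence is silently corrected in programming, a reader of the public SAP cannot tell which rule produced the reported model.

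Two editorial matters sit in the same paragraph. It cites Section 6.5 for missing covariate data, but 6.5 is Subgroup Analyses and multiple imputation is in 6.4. The term *key clinical covariates* is not defined in the documents supplied. The Section 6.1 set is its natural meaning.

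**Working it through.** The plan has no derived figure to reproduce, since 0.10 is a chosen threshold. The check is of the rule's direction, then of how often each version keeps a covariate.

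**1. Text.** The named method keeps small p-values, the inclusion sentence keeps large ones, and the Section 6.5 rule acts on small ones. Two of the three agree, and the inclusion sentence is the exception.

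**2. Single-test retention.** For a two-sided Wald test with expected z equal to m, the critical value at 0.10 is 1.645. As written, P(kept) = P(|Z + m| < 1.645); under the usual rule it is 1 minus this.

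| m | Kept as written (p > 0.10) | Kept under usual rule |
|---|---|---|
| 0 | 90.0% | 10.0% |
| 1 | 73.6% | 26.4% |
| 2 | 36.1% | 63.9% |
| 3 | 8.8% | 91.2% |
| 4 | 0.9% | 99.1% |

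If all ten named candidates were unrelated to the outcome, 10 × 0.90 = 9 would be expected in the model as written, against 10 × 0.10 = 1 under the usual rule.

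**3. Dependence on stratum size.** Assume a binary covariate with prevalence 35% and an event rate of 23% (neither is in the documents). Then expected z ≈ ln(OR) × √(N × 0.35 × 0.65 × 0.23 × 0.77). For OR 1.5 and N = 2000 this is 0.405 × √80.6 = 3.64.

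| N | OR 1.3: z, kept as written | OR 1.5: z, kept as written |
|---|---|---|
| 400 | 1.05, 72% | 1.63, 51% |
| 1000 | 1.67, 49% | 2.57, 18% |
| 2000 | 2.36, 24% | 3.64, 2% |
| 3000 | 2.88, 11% | 4.46, 0.2% |

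**4. A second literal reading.** Suppose backward elimination is run to completion and the sentence is applied to what is left. In 300 simulated logistic data sets (N = 2000, ten independent candidates, four of them predictive), no term with p > 0.10 remained at the end of any run, as the algorithm guarantees. No candidate would be added. If *key clinical covariates* means the Section 6.1 set, the sensitivity model is then simply the main model.

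**5. Possible effect on the treatment estimate (illustration only).** The simulation used 300 runs per setting, a true treatment OR of 1.00, ten binary candidates of prevalence 35%, four of them prognostic, and an event rate of 23%. Hospital clustering, imputation and the Section 6.1 covariates were left out. The intended rule is the right comparator. Imbalances are in percentage points between arms.

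| N, covariate OR | Imbalance | Treatment OR: literal / intended / full | Literal ÷ intended |
|---|---|---|---|
| 2000, 1.5 | none | 0.989 / 0.991 / 0.990 | 1.00 |
| 2000, 1.5 | two +10, two −10 | 0.991 / 0.989 / 0.989 | 1.00 |
| 2000, 1.5 | one +5 | 1.011 / 0.992 / 0.991 | 1.02 |
| 2000, 1.5 | all four +5 | 1.074 / 0.993 / 0.992 | 1.08 |
| 2000, 1.5 | all four +10 | 1.166 / 0.995 / 0.993 | 1.17 |
| 400, 1.5 | all four +5 | 1.065 / 1.027 / 1.007 | 1.04 |
| 400, 1.3 | all four +5 | 1.031 / 1.022 / 1.001 | 1.01 |

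In the balanced case the number of prognostic candidates kept, out of four, as written against intended, was 2.9 against 1.2 (N = 400, OR 1.3), 2.0 against 2.0 (400, OR 1.5), 0.7 against 3.3 (1000, OR 1.5) and 0.1 against 3.9 (2000, OR 1.5). The first of each pair agrees with step 3, for example 4 × 0.72 = 2.9.

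**The case against.** The strongest reply is that this is a one-character slip with its correction beside it: backward selection has a fixed direction, and any statistician would read it that way. The analysis is a secondary one, done where feasible, and reporting the treatment estimate at each step serves its purpose whichever way the sign runs. This stands as a limit on the harm. It does not settle which model is the final sensitivity model, and it leaves the programmer to depart from the SAP without a documented basis.

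A second reply is that the consequence depends on the reading and on stratum size. This also stands. In a small stratum with weak covariates the written rule can keep more prognostic candidates than the usual rule (2.9 against 1.2 at N = 400, OR 1.3), because the usual rule has little power there. Under the other literal reading nothing is added.

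A third reply is that the illustrated shifts are hypothetical and mostly small beside sampling error. With the same assumed inputs, N = 2000 and 1:1 arms, the unclustered standard error of the log OR is 1/√(2000 × 0.25 × 0.23 × 0.77) = 0.106, so a 95% interval spans a factor of about exp(1.96 × 0.106) = 1.23 either way. That is fair, and the conclusion does not rest on the simulation.

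Finally, the parent Phase 1 SAP was not available and may state the rule or define the forced covariates. If it states the rule correctly, this addendum conflicts with it and still needs correcting.

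**Conclusion.** The concern holds, as a minor point. The inclusion rule in Section 6.1.1 is reversed relative to the method named in the same paragraph, and nothing supplied corrects it. This rests on the text alone.

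The retention probabilities in step 2 need no trial data. Any shift in the treatment estimate depends on covariate imbalance, covariate strength and payer-stratum size, none of which the documents give. Under the assumptions shown, the shift is nil with balance, about 2% in the odds ratio with one candidate off by 5 points at N = 2000, and 8% to 17% at N = 2000 only when all four prognostic candidates are imbalanced the same way. Those last are unfavourable cases, not expectations.

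The main Section 6.1-adjusted results are unaffected. The wrong cross-reference is confirmed. The undefined term is a query for the sponsor.

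**What to change.** In Section 6.1.1, state that additional candidates with p < 0.10 are retained and those with p ≥ 0.10 are removed, after the sponsor has confirmed this against the parent Phase 1 SAP. In the same paragraph, cite Section 6.4 instead of 6.5 for missing covariate data, and say whether *key clinical covariates* means the Section 6.1 set forced into every step. If the models have already been run, record which rule the programs applied.

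The cost is wording only: one inequality sign, one section number and one confirmed definition. No data collection, sample size or main analysis changes.
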